Appendix: Results summary tables (page 17)

Code for imputation (R) (page 23)

ABBREVIATIONS

| | |
|----------|---|
| AUC | Area under the curve |
| AUSDRISK | The Australian type 2 diabetes risk assessment tool |
| BMI | Body mass index |
| CGM | Continuous glucose monitoring |
| CR | Calorie restriction (30%) |
| dCR | Delayed calorie restriction (30% calorie restriction, 12pm – 8pm) |
| eCR | Early calorie restriction (30% calorie restriction, 8am – 4pm) |
| HbA1c | Glycated haemoglobin |
| iAUC | Incremental area under the curve |
| PP | Post-prandial |
| SAP | Statistical analysis plan |
| T2DM | Type II diabetes mellitus |

PREFACE

This statistical analysis plan (SAP) describes the planned analyses and reporting for the OMIT study to compare early calorie restriction (eCR) or delayed calorie restriction (dCR) versus calorie restriction (CR) without time limits in men and women with overweight and obesity and elevated fasting blood glucose. The purpose of this SAP is to outline the considerations and the pre-specified analyses for the OMIT study.

The project is funded by the NHMRC Ideas grant #2012569 awarded to [name].

This study has been approved by the University of Adelaide Human Research Ethics Committee (HREC 2022-199).

Study Rationale & Objectives

Background/Rationale

Caloric restriction (CR) is widely recognised for its ability to reverse or alleviate the metabolic health consequences of obesity, and even extends lifespan in mouse models. Time-restricted eating (TRE), whereby food intake is typically limited to 8 h eating window during the day may be a novel, alternative dietary strategy to improve cardiometabolic health individuals with obesity. Recent studies in mice suggest that CR+TRE was able to extend the health benefits of CR alone, with the maximal effect noted when the meal timing period was initiated at the onset of the active phase. The ideal meal timing to initiate TRE is under-researched in humans. The proposed randomised clinical trial will be the first to determine whether CR+TRE that is initiated early in the day (early CR) or delayed CR is able to extend the health benefits of CR alone in humans.

Primary Objective

- To establish whether early or delayed time-restricted eating plus calorie restriction, improve markers of type 2 diabetes, compared with calorie restriction alone.

Secondary Objective

- To explore the effect of time-restricted eating on insulin and gut peptide AUCs, 24-h glycaemia by CGM, and cardiometabolic health biomarkers.

Study Outcomes

Primary efficacy outcomes

- The difference in percentage change from baseline in the mean 2-hour post-meal glucose AUC levels after eight weeks of (i) time restricted (early) versus non-time restricted dieting and (ii) time restricted (delayed) versus non-time restricted dieting, in men and women with obesity.

Secondary efficacy outcomes at 8 weeks

- Changes in...
 - PP insulin AUC
 - fasting insulin,
 - fasting glucose, and
 - HbA1c.

Exploratory mechanistic outcomes: at 8 weeks

- Change in...
 - PP glucose and insulin AUCs for each meal
 - 24-h glucose by CGM (mean and iAUC),
 - nocturnal glucose by CGM (mean)
 - insulin sensitivity calculated by the Matsuda index
 - gut peptides (AUCs and iAUC),
 - insulin secretion by C-peptide,
 - HOMA-IR
 - 24-h profiles of glycaemia by CGM (i.e. time-above/below/in range, MAGE, MODD)

Exploratory outcomes

- Listed in the Appendix, see tables A4 & A5.

[figure not shown]
Compliance outcomes

- Self-reported adherence over the eight weeks
- Adherence to eating window assessed by smartphone application and diet diaries.
- Protocol deviations arising from inappropriate inclusion (ie contradicting inclusions/exclusion criteria) will be listed.

STUDY DETAILS

Study Design: OMIT is a three-arm parallel, single-blinded, single-centre randomised controlled clinical trial.

Figure 1: Schedule of assessments

Study Population

Inclusion criteria

Study participants will be aged 35 to 75 years and overweight (BMI: >25.1 but < 45kg/m²) with elevated waist circumference, score 12 or greater on the AUSDRISK questionnaire and have elevated fasting blood glucose (≥5.6 mmol/L).

| Elevated risk for waist circumference | Male(cm) | Female (cm) |
|--|----------|-------------|
| Caucasian/African | >94 | >80 |
| Asian | >88 | >74 |
| South Asian, Aboriginal/Torres Strait Islander | >79 | >70 |

Exclusion criteria

A personal history/diagnosis (self-reported) of:

- diabetes (type 1 or 2)
- major psychiatric disorders (schizophrenia, major depressive disorder, bipolar disorder, eating disorders)
- gastrointestinal disorders/disease (including malabsorption)
- haematological disorders (i.e. thalassemia, iron-deficiency anaemia)
- insomnia
- obstructive sleep apnea
- night eating syndrome
- currently receiving, or have received treatment/diagnosis of cancer in the past 3 years (excluding non-melanoma skin cancer)
- significant liver or kidney diseases that require ongoing medical care
- previous or planned gastro-intestinal surgery (including bariatric surgery)
- Congestive heart failure (NYHA stage 2 or above)
- Previous myocardial infarction or significant cardiac event ≤ 6 months prior to screening
- Previous cerebrovascular event ≤ 12 months prior to screening
- Any autoimmune disease (i.e. rheumatoid arthritis)
- Coeliac disease/gluten allergy
- Nut allergy
- other conditions deemed unstable by the study physician.

Currently taking the following medications:

- used, or known, to lower blood glucose, or antidiabetic medications, including, but not limited to: SGLT2 inhibitors, metformin, sulfonylureas, glucagon-like peptide-1 analogues [i.e. exenatide], thiazolidinediones or DPP-IV inhibitors [i.e. 'gliptins']
- affecting weight, appetite or gut motility, including, but not limited to: (domperidone, cisapride, orlistat, phentermine, topiramate).
- Diuretics (i.e. thiazides) or combination blood pressure medications containing a

diuretic

- Beta-blockers
- Glucocorticoids
- Anti-epileptic medications (i.e. pregabalin and gabapentin)
- Tricyclic antidepressants
- Some serotonin and norepinephrine reuptake inhibitors (i.e. vortioxetine, mirtazapine and venlafaxine)
- Regular use of benzodiazepines or other sleep aids, including melatonin
- Antipsychotic medications
- Opioid medications unless combined with paracetamol in a single formulation and used occasionally on a PRN basis

Participants who are taking stable doses (i.e. > 3 mo.) of androgenic medications (i.e. testosterone), blood pressure medications (not listed above), lipid medications, thyroid medication, SSRI's or SNRIs (with the exception of those mentioned above) or benign prostatic hyperplasia will not be excluded.

Additional exclusion criteria include:

- AUSDRISK score of < 12
- Fasting blood glucose levels < 5.6
- Score \geq 30 on Kessler Psychological Distress scale
- do not eat for 12 hours per day on an average of 5 or more days per week
- have extreme or restricted patterns of eating (i.e. following an intermittent fasting diet) or already engage in CR or TR
- night shift-workers (>3 shifts per month)
- pregnant, planning a pregnancy or currently breastfeeding
- those who have lost or gained >5% of body weight in the last 6 months
- donated blood in past 3 months
- current smokers of cigarettes/marijuana/e-cigarettes/vaporisers
- anyone unable to comprehend the study protocol or provide informed consent (i.e. due to English language or cognitive difficulties)
- do not own, or are not comfortable using, a smartphone and applications

Individuals with dietary restrictions or practices, including vegans and those with gluten or nut allergies will be excluded. Less restrictive dietary practices including vegetarians and those with lactose intolerance or specific dietary dislikes will be accommodated.

Pre-planned Sample size

An expected group difference is 0.46 mmol/L at 2-hrs after a glucose tolerance test (1). Our past data, DIRECT study (2) showed a mean glucose concentration of 7 mmol/L at two hours post meal. We note that $0.46/7.0$ is a 6.5% reduction. T4DM powered for a 0.6 mmol/L between group difference, which is approximately 6% change from baseline in a population including individuals with diabetes (3). We thereby assumed the MCID to be a 6% reduction from baseline in mean post meal AUC and use log (AUC) to estimate of the percentage difference between groups (4).

Using data from the DIRECT study (2), the SD of the log (meal test AUC) is expected to be 0.152 and pre-post AUC correlations were 0.87 at breakfast and 0.92 at dinner.

With $N=114$ (38 per group, randomized 1:1:1), a within-group SD of 0.152, pre-post correlation of at least 0.85 and a drop-out rate less than 10%, there is >80% to detect a difference of 0.06 in log-transformed AUC in a baseline adjusted ANCOVA ($\alpha = 0.027$ two-sided) (5).

Sample size adaption

None

Randomization details

Stratified random length blocked randomisation by sex (male or female) and fasting plasma glucose (≤ 6.0 vs >6.0 mmol/L)

STATISTICAL CONSIDERATIONS

Estimand Considerations

| | |
|--|---|
| Study objective 
 - To establish whether early or delayed time-restricted eating plus calorie restriction (eCR, dCR), improve markers of type 2 diabetes, compared with calorie restriction (CR) alone | |
| Estimand 
 - The difference in percentage change from baseline in the mean 2-hour post-meal glucose AUC levels after eight weeks of time restricted versus non-time restricted dieting, in obese men and women | |
| Treatment 
 - eCR (30% calorie restriction, 8am – 4pm); - dCR (30% calorie restriction, 12pm – 8pm); - CR (30% calorie restriction, 8am-8pm); Control group | |
| ESTIMAND | ANALYSIS |
| Target population 
 - Men and women with obesity and elevated fasting blood glucose | Analysis set 
 - All randomized - Initiated diet |
| Variable 
 - Glucose AUC over 3 meals (breakfast, lunch, dinner). | Outcome measure 
 - Blood glucose AUC - Measured at 0,30,60,120 post-meal - Averaged over three meals |
| Handling of inter-current events 
 1. Death (while on treatment strategy, or “while alive”) 2. Discontinuation: other reason (while on treatment strategy) 3. Discontinuation: dislike of diet (treatment policy strategy) 4. Lost-to-follow-up no reason provided (treatment policy strategy) | Handling of missing data 
 1. Death believed not to be relevant for this study, included for completeness. 2. All individuals discontinuing early will (i) be invited to attend the week 6 assessment for fasting bloods and body weight only, (ii) asked whether the reason for discontinuation is due to allocated diet. 3. Missing-at-random will be assumed for individuals who do not specify whether discontinuation was due to diet, or when the reason was not due to the diet. 4. For individuals who discontinued due to the diet a missing-not-at-random assumption will be made, assuming zero adherence after discontinuation, and conditional on adherence missing-at-random assumed to impute week 8 outcomes. |

| | |
|---|--|
| | 5. Imputation is by treatment group with individuals imputed in the groups they were allocated to. |
| Population level summary measure 
 - Mean between group differences in baseline adjusted log-transformed (within-individual) mean post-meal glucose AUC, of the time-restricted groups versus the control (non time-restricted) group. | Analysis approach 
 - Group differences of log transformed mean post-prandial AUC will be estimated using a single linear regression with a treatment (three levels) and baseline log transformed mean post-prandial glucose AUC and stratification factors (sex and fasting plasma glucose). |

Hypothesis testing framework: All analyses are to test for superiority of eCR and dCR over CR.

Analyses: No interim analyses are planned. The analysis of the primary outcome will be conducted after the final subject has completed their 8 week assessment and the blood samples assessed for glucose concentrations.

Error Control: There are two primary comparisons, eCR vs CR and dCR vs CR with a common control and thereby use a Dunnett multi-test adjustment that controls the familywise error rate at 0.05 (two-sided) when each pairwise test uses an alpha of 0.027 (two-sided).

There are four secondary efficacy outcomes that will be tested to support a confirmatory finding: (i) PP insulin AUC, (ii) fasting insulin, (iii) fasting glucose, and (iv) HbA1c. An ordered testing procedure with per comparison (eCR vs CR and dCR vs CR) will be applied testing these four secondary outcomes in the order listed here, testing each subsequent outcome only if the previous outcome (and primary outcome) rejected the null. This procedure is applied separately for each comparison: eCR vs CR and dCR vs CR. The same pairwise alpha level, 0.027 (two sided), as the primary outcome will be applied to ensure that the familywise error rate is controlled at 0.05 (two-sided).

Standard multiplicity unadjusted 95% confidence intervals will be reported for all comparisons.

Covariate adjustment: All comparisons of treatment effect will include adjustment for...

1. The outcome variable's baseline assessment if appropriate,
2. Stratification factors (sex and baseline fasting plasma glucose as a continuous variable)

Sensitivity Analyses: A best-worst case sensitivity analysis will be performed for the analysis of the primary outcome and secondary efficacy outcomes.

- For all individuals missing the week 8 assessment in the CR (control) group the outcome will be imputed assuming missing-at-random. In other words, as if each individual's mean adherence was continued, or the cohort's mean adherence if no adherence data is available for an individual.
- For individuals missing the week 8 assessment in the eCR and dCR groups their outcome, a missing-not-at-random assumption will be applied by assuming zero adherence and outcomes imputed thereafter, i.e., assuming missing-at-random conditional on zero subsequent adherence.
- These assumptions will be made irrespective of the stated reason for diet discontinuation.

A secondary, complete-case sensitivity analysis will be performed for the analysis of the primary outcome and secondary efficacy outcomes in this analysis individuals with both baseline and week 8 assessments will only be included for each analysis.

As additional analysis will explore the treatment effects within subjects who were adherent to the protocol using data collected with the MyCircadianClock app plus the dietary checklists. This analysis will be reported in a secondary mechanistic publication of this study.

STATISTICAL METHODS

Primary Outcome

The primary analysis of the primary outcome is a covariate adjusted linear regression of the differences in PP glucose log AUC at 8 weeks from baseline. Covariates included will be treatment (three groups), baseline glucose log AUC, sex and fasting plasma blood glucose (as a continuous linear variable). Visual inspection of the residual distribution will be used to determine if assumptions of normality and the absence of a variance-mean association appear to be violated. If assumptions appear violated a generalized linear models will be considered with differing link functions will be considered and presented as sensitivity analyses. Given the limited sample size, no subgroup analyses are planned.

This analysis will be performed in all randomized individuals with individuals using multiple imputation using chained equations within treatment groups and combined using Rubin's rules. The variables used in the multiple imputation are age and sex; baseline and week 8 assessments of weight, PP glucose and insulin AUC (per meal), fasting glucose, fasting insulin and HbA1c; and the self-reported adherence over the 8 weeks and reason for discontinuation (related/unrelated to diet) if applicable. All concentrations will be imputed on the log scale, with the 3-meal mean of PP glucose and insulin AUC being calculated on the original scale after a back-transformation. Compliance will be imputed as per the intercurrent event strategies and the average compliance calculated over each period. Imputation will use multiple chained equations (*mice* R package), details of which are attached separately (file: *OMIT – Imputation code 2024-12-18.r*).

Secondary Efficacy Outcomes

The four secondary efficacy outcomes used in the multiple imputation of the primary outcome will be assessed using the same methodology as for the primary outcome, i.e. covariate adjusted linear regressions with multiple imputation for missing data.

Exploratory Outcomes

Exploratory outcomes will also be analysed using baseline and stratification factor adjusted linear regressions. The weight and PP glucose and insulin meal specific analyses will be performed in the imputed data sets. All other outcomes will be analysed using complete case data sets.

Safety Outcomes

Summaries, for all adverse events and for those events believed to be related to the intervention, will be reported. In both cases, if an individual has experienced the adverse event on multiple occasions, only the event with the maximum grade will be reported.

When there are at least four individuals who experience a particular adverse event, a Fisher exact test will be conducted comparing the rates of occurrence (irrespective of grade) between the two intervention groups. No adjustments for multiple testing will be performed.

[figure not shown]
STUDY SUMMARY TABLES

Descriptive Statistics: A CONSORT flow chart will present all individuals screened through to randomization and week 8 assessment will be presented (Figure 2). The number of individuals who discontinue their allocated intervention and/or withdraw from the study, the week and reason for discontinuation will be reported.

Descriptive summary statistics will be reported for baseline characteristics of all individuals who were randomized. In addition to baseline glycemia indices we will report on age, sex, menopausal status, AUSDRISK, body composition, markers of CVD risk, sleep, activity and appetite measures. For continuous variables means, standard deviations, medians and ranges will be reported, and for discrete variables frequency and percentages will be reported. No demographic summary statistics were collected for the screened cohort.

Results tables presenting the analyses of the primary, secondary and exploratory outcomes are presented in Appendix A.

Figure 2: CONSORT flow chart of OMIT study.

REFERENCES

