  # var. <- w8.list[1]

  if (!var. %in% meal.list) {

    fm. <- paste(var., "~ (", paste(c(

      sub('w8', 'w0', var.)

      , c('sex', 'adherence', "fasting.glucose.w0", "glucose.auc.w0", "insulin.auc.w0")

      , w8.list[!w8.list %in% c(var., meal.list)]

      , c("glucose.auc.w8", "insulin.auc.w8")

    ), collapse=' + '), ')')

    fm.list <- c(fm.list, as.formula(fm.)); rm(fm.)
  }
}

```

```

} else {

  fm. <- paste(var., "~ (" , paste(c(

    sub('w8', 'w0', var.)

    , c('sex', 'adherence', 'fasting.glucose.w0')

    , w8.list[!w8.list %in% c(var.)]

    ), collapse=' + '), '))

  fm.list <- c(fm.list, as.formula(fm.)); rm(fm.)

}

}; rm(var.)

fm.list <- as.list(fm.list)

names(fm.list) <- c(w0.list, w8.list)

```

```

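### The best-worst sensitivity analysis is not guaranteed to be a worst case for eCR and dCR: its penalty runs through an adherence slope estimated within each arm, and nothing fixes that slope's size or sign

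*SAP*

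**What the plan says.** Under Sensitivity Analyses, the SAP plans a best-worst analysis of the primary and secondary efficacy outcomes. Missing CR outcomes are imputed as missing at random (MAR). Missing eCR and dCR outcomes are imputed "assuming missing-at-random conditional on zero subsequent adherence", whatever the stated reason for stopping. The Estimand Considerations table adds: "Imputation is by treatment group with individuals imputed in the groups they were allocated to". It also says that people who stop early are invited back for fasting bloods and weight only, so no post-meal AUC is planned off diet.

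The imputation code does the same:
- mice is run separately for groups A, B and C.
- For drop-outs classed as diet-related, adherence scores after the drop-out week are set to 0, and the outcome itself is not shifted.
- Mean adherence is computed as (w2 + w4 + 2*w8)/4.
- Each week-8 meal formula includes "c('sex', 'adherence', 'fasting.glucose.w0" among its terms, so adherence is a single linear main effect.

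I found no delta shift, return-to-baseline rule or reference-based rule in the text or the code.

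**The concern.** A best-worst analysis is read as a bound: if the finding survives it, informative drop-out is taken not to explain the finding. That reading needs the missing eCR and dCR outcomes to be set worse than under MAR. Here they are worse only if the arm's estimated adherence slope points the expected way and is steep enough. If the slope comes out flat or reversed, the table labelled best-worst shows a result equal to, or better than, one that assumes continued adherence. The only other planned missing-data sensitivity analysis is complete-case, which does not test informative drop-out.

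**Working it through.** **Inputs from the SAP (Pre-planned Sample size).** Size "38 per group, randomized 1:1:1"; "a drop-out rate less than 10" per cent; "a within-group SD of 0.152"; "pre-post correlation of at least 0.85"; power "to detect a difference of 0.06 in log-transformed AUC"; pairwise alpha 0.027 two-sided.

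**Assumptions not in the SAP.** Adherence runs 0 to 4 (five response levels, with 0 worst as the code says). Completers' adherence has mean 2.5 to 3.6 and SD 0.4 to 1.0.

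**1. The plan's power figure.** Residual SD = 0.152 × √(1 − 0.85²) = 0.0801. Completers per arm = 38 × 0.9 = 34.2, taken as 34. Standard error of the contrast = 0.0801 × √(2/34) = 0.0194. Power (normal reference) = 0.81, so the stated figure of more than 80% reproduces.

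**2. Precision of the penalty.** Regress week-8 log AUC on baseline and mean adherence in 34 completers (31 residual df). The penalty is the predicted rise in log AUC when adherence moves from the arm mean m to 0:

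SE(penalty) = m × 0.0801 / (SD_adh × √31)

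For m = 3.2 and SD 0.6: 3.2 × 0.0801 / (0.6 × 5.568) = 0.077. With a true penalty of 0.06, t = −0.06/0.077 = −0.78, and the chance of a zero or favourable penalty is 0.22.

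| Adherence mean / SD | SE of penalty | P(penalty ≤ 0), true 0.06 | true 0.03 |
|---|---|---|---|
| 3.6 / 0.4 | 0.129 | 0.32 | 0.41 |
| 3.2 / 0.6 | 0.077 | 0.22 | 0.35 |
| 3.0 / 0.8 | 0.054 | 0.14 | 0.29 |
| 2.5 / 1.0 | 0.036 | 0.05 | 0.21 |

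If adherence is unrelated to outcome, the chance is 0.50.

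**3. Check by simulated imputation.** Settings: 600 trials per scenario, 34 completers, 4 missing, 20 imputations, true penalty 0.06. Over the first three adherence distributions, the imputed penalty was zero or favourable in 15 to 34% of trials. At 3.2/0.6 it was 25% with normal imputation and 27% with predictive mean matching. The code leaves the method at the package default. If that is predictive mean matching, donors are completers of the same arm, and the average penalty shrinks from 0.06 to about 0.035 to 0.046.

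**4. Dilution by the averaged score.** For someone fully adherent until stopping:
- stopping before week 2: (0 + 0 + 0)/4 = 0
- stopping in week 3: (4 + 0 + 0)/4 = 1
- stopping in week 5: (4 + 4 + 0)/4 = 2

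Only the earliest drop-outs are imputed at zero.

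**5. Effect on the contrast.** With 4 of 38 missing in an arm, a 0.06 per-person penalty moves the contrast by 0.06 × 4/38 = 0.006, against a standard error of 0.019.

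**6. Delta needed to lose significance.** The critical value at alpha 0.027 is 2.21, so the contrast must fall to 2.21 × 0.0194 = 0.043. From the design effect of 0.06 that is a shift of 0.017. Per missing person it is 0.017 / (4/38) = 0.16, counted from values imputed under MAR and holding the standard error fixed.

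**The case against.** The rule is stated, pre-specified and coded, and several points count against making too much of it.

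- **The adherence distribution is assumed.** A reader might infer that completers are nearly all adherent, with almost no data near zero. The SAP does not say so. With a wide spread (2.5/1.0) the chance of a wrong sign at a true loss of 0.06 is only 5%. This stands, and is why a range is given.
- **Other week-8 variables enter the meal formulas.** Off-diet fasting values from discontinuers could inform their imputed AUC. The code ignores week-8 fasting glucose when deciding who has week-8 data, which suggests that some discontinuers have it. The SAP does not say that week-6 values enter as week-8 values, so this is unresolved. These extra terms also leave fewer residual degrees of freedom than the 31 used above.
- **The calculation moves people all the way to zero.** For those who stop at weeks 4 to 7 the code roughly halves that move, so the penalty and its SE are about half as large. The share with the wrong sign is unchanged.
- **Rubin's rules carry the slope uncertainty.** A reader might infer that a positive finding would be called robust without having been challenged at all. That goes too far. In a simulation with a true effect and loss of 0.06, normal-model imputation, 4 of 38 missing and adherence set fully to zero, the standard error rose from about 0.020 to 0.022 to 0.025. Of significant primary results, 62 to 78% stayed significant. A return-to-baseline rule (assuming a CR benefit of 0.06) kept 67 to 72%, so on average the planned analysis was about as demanding. However, among trials with a wrong-sign penalty 93 to 99% of significant results survived, and if adherence was only halved 85 to 91% survived overall.

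What remains is that the direction of the stress test is left to the estimated slope.

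**Conclusion.** The concern holds in limited form. Neither the SAP text nor its code guarantees that the best-worst analysis is unfavourable to eCR and dCR. For a true loss of 0.06, the penalty would be zero or favourable in roughly 5 to 32% of arms, conditional on the assumed adherence distributions and about 34 completers per arm. The averaged score weakens the penalty further for later drop-outs.

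The documents do not support reading this as a flaw in the primary estimate. The primary analysis applies zero adherence only to diet-related discontinuers. At the planned drop-out, the whole effect on the contrast is about a third of a standard error (0.006/0.019). What is affected is the claim of robustness to informative drop-out, mainly for post-meal outcomes. The point does not depend on which drop-outs the code selects for the rule.

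**What to change.** In Sensitivity Analyses, add (or make the lead best-worst analysis) a version independent of the adherence slope:

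1. For eCR and dCR participants missing week 8, impute week-8 log AUC as their own baseline log AUC plus residual error, with CR imputed under MAR as now. This retains no benefit, so it penalises an arm whenever its completers improved on average.
2. Follow it with a delta series on the log scale, added to the imputed eCR and dCR values and continued until significance at 0.027 is lost. Its direction is fixed by construction. Starting from MAR imputations, the grid must extend well beyond +0.06, to about +0.16 or more at the design effect with 4 of 38 missing.
3. Keep the zero-adherence version as a further sensitivity analysis.

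The cost is some SAP wording and a few lines of post-processing of the imputations; no new data are needed. The downside is one more sensitivity table and possibly less favourable results.
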